- Glu: glutamate
- Gln: glutamine
- GPC: glycerophosphocholine
- GSH: glutathione
- HARDI: high angular resolution diffusion imaging
- mI: myo-Inositol
- Lac: lactate
- MD: mean diffusivity
- MRI: Magnetic Resonance Imaging
- MRS: Magnetic Resonance Spectroscopy
- NAA: *N*-acetylaspartate
- NAAG: *N*-acetylaspartylglutamate
- NAF: National Ataxia Foundation
- PC: phosphocholine
- PCr: phosphocreatine
- PE: phosphoethanolamine
- RD: radial diffusivity
- ROC: receiver operating characteristic
- RSN: resting-state network
- SARA: Scale for the Assessment and Rating of Ataxia
- SCA: spinocerebellar ataxia
- sIns: scyllo-inositol
- SNR: signal to noise ratio
- Tau: taurine
- tCr: total creatine, creatine + phosphocreatine
- UMN: University of Minnesota
- VOI: volume-of-interest

STUDY SUMMARY

Study Title	Clinical Trial Readiness for SCA1 and SCA3
Study Design	Observational, longitudinal
Primary Objective	To validate MR morphological (Volumetry/voxel based morphometry/diffusion), biochemical (MRS), and functional (resting-state fMRI) biomarkers in spinocerebellar ataxia 1 (SCA 1) and spinocerebellar ataxia 3 (SCA 3) at premanifest and early stage
Secondary Objective(s)	To study the relationship between these MRI/MRS measures and clinical status of subjects
Research Intervention(s)/Investigational Agents	
 • Longitudinal MRI/MRS scans at 3T • Clinical evaluation: Standardized ataxia scale (SARA)
Scientific Assessment	Nationally-based, federal funding organizations
IND/IDE # (if applicable)	N/A
IND/IDE Holder	N/A
Investigational Drug Services # (if applicable)	N/A
Study Population	Patients with ataxias and healthy subjects, 18 years or older
Local Sample Size (number of participants recruited locally)	30

1.0 Objectives

1.1 Purpose: The **primary goal** of this study is to validate MR morphological (Volumetry/voxel based morphometry/diffusion), biochemical (magnetic resonance spectroscopy, MRS) and functional (resting-state fMRI) biomarkers in premanifest/early SCA1 and SCA3. The **secondary goal** is to evaluate the relationship of these MR measures with the clinical status of subjects with SCA1 and SCA3. Such morphological, biochemical and functional measurements can provide non-invasive biomarkers to monitor progression of the neurodegenerative pathology, as well as serve as secondary outcome measures in future clinical trials of ataxias.

2.0 Background

2.1 Significance of Research Question/Purpose:

SCAs are hereditary movement disorders in which cerebellar neurodegeneration results in progressive balance and coordination deficits (1). They are disabling, fatal and cause significant physical, psychological, social and economic burdens to patients and caregivers. While they are currently untreatable, neuronal and motor dysfunction is reversible in SCA mouse models (2, 3). Furthermore, advances in understanding of molecular mechanisms of common SCAs (1, 4) have raised a realistic hope for the development of effective therapeutic interventions (5). For example, therapies based on gene silencing show great promise for the polyglutamine (CAG repeat expansion) disorders SCA1, 2, 3 and 6 (3, 6, 7). Therefore, the need for establishing imaging biomarkers to monitor cerebral pathology is more pressing than ever.

SCAs 1, 2, 3, and 6 are the most prevalent SCAs in the US (8) and Europe (9). Of these, SCA1 progresses more rapidly than SCA2, 3 and 6 (8, 9), allowing shorter clinical trials, and SCA3 is the most prevalent SCA worldwide (8-10), allowing the recruitment of a large number of patients into clinical trials. SCA1 and SCA3 are relentlessly progressive, disabling, and eventually fatal neurodegenerative diseases with no efficacious treatments other than supportive therapy (11, 12). Importantly, several clinical trials for disease modifying therapies in SCA1 and SCA3 are anticipated within the next 5 years. Most clinical trials, thus far, have included SCA patients at all stages of disease and phenotypes, and may therefore have missed a therapeutic window. Mounting evidence argues for administration of therapies in the earliest, including *premanifest*, stages of neurodegeneration. Namely, inducible genetic mouse models of polyQ diseases including SCA1 (2, 13-15) show disease reversibility early on, which is lost as the disease progresses, with increasing cellular dysfunction and cell death in the brain. Consistent with this, efficacy of a novel antisense oligonucleotide (ASO) treatment doubled when administered in the pre-symptomatic vs. symptomatic phase in another hereditary neurodegenerative disease (16, 17). Hence, in this project we will focus on premanifest gene carriers who have no ataxia (score on the Scale for the Assessment and

Rating of Ataxia [SARA] <3; maximum score = 40) (18, 19) and early-stage patients (SARA 3-9).

This study will define characteristics of the earliest disease progression measurable by MRI and MRS, with a goal to predict disease onset in premanifest individuals based on a multi-parametric model that incorporates imaging biomarkers. While we do have an existing predictive model to estimate the future age at onset for the major SCAs based on CAG repeat size and current age (20) there is great variability in onset ages between patients with the same CAG repeat, even within the same family. Therefore, measuring cerebral disease onset by noninvasive imaging is bound to substantially improve the estimation of onset age of manifest disease and allow recruitment of those premanifest patients who are closest to disease onset into future trials. Despite wide utility of brain MR biomarkers in neurological disorders, an advanced, 1-hour, 3T morphometric, biochemical and functional imaging marker protocol has not been validated in a multi-site trial setting and is likely to serve as a template in future neurodegenerative disease trials.

This protocol application is for local MRI/MRS acquisition and centralized data analysis under a recently funded multi-site U01 grant (U01NS104326-01, contact PI: [name], Houston Methodist Research Institute; [name], MPI) for clinical trial readiness in SCA1 and SCA3. The Center for Magnetic Resonance Research (CMRR) is the lead imaging site for analysis of multi-site MRI data. Subjects will be identified by the Clinical Research Consortium for Studies of Cerebellar Ataxias (CRC-SCA) investigators, evaluated clinically and referred for MR scanning to select imaging sites. All imaging will be done under local IRB approval.

2.2 Preliminary Data:

Under a currently active IRB protocol (IRB# 0502M67488), we completed a study analyzing high angular resolution diffusion imaging (HARDI) data acquired from early-stage patients with SCA1, 2, 3, 6, and matched healthy controls (N=8-9 per group) at 3T. We demonstrated alterations in corticospinal tracts, cerebellar peduncles, pontine tract, cerebellar cortex, and thalamus in early stage SCA1 (SARA = 9 ± 5 , mean \pm SD) and localized differences in the cerebellar peduncles in early stage SCA3 (SARA = 6 ± 3 , mean \pm SD). Between-session test-retest CVs for fractional anisotropy (FA) obtained from HARDI data was <3%. Importantly, we found 11% lower FA in 3 premanifest SCA1 mutation carriers (SARA=0-1) vs. 9 controls ($p < 0.05$, one-tailed two-sample unequal variance t-test) in the regions that demonstrated lower FA in the entire SCA1 cohort.

Under the same IRB protocol, we completed a single-site MRS study with 100 subjects (SCA1, 2, 3, 6 [58% of patients with SARA<10] and controls), including 9 premanifest mutation carriers (SARA=0-1). MRS data were acquired at 7T from 3 volumes of interest (VOIs). We utilized a distance weighted discrimination (DWD) approach (21) that combined data from the

3 VOI. DWD is a machine learning algorithm that finds an optimized hyperplane separating two or more groups. This analysis showed: **1)** subjects with SCA1 (SARA=8±4, mean±SD) and SCA3 (SARA=7±3) were distinguished from controls with 95-98% correct classification rate; **2)** classifications were driven strongly by metabolite levels in the cerebellar WM and pons, which showed that data collected from these 2 VOI will be sufficient for future trials; **3)** premanifest mutation carriers were distinguished from controls if the time-to-onset, estimated based on CAG repeat size and current age (20), was 10 years or less, which was the case for 6/9 cases in this cohort. These data indicate that neurochemical abnormalities can be detected up to 10 years from onset of ataxia. Even though these data were acquired at 7T, test-retest reproducibility for the neurochemicals that drive these classifications (NAA, *myo*-inositol, glutamate, creatine) is the same at 3T and 7T (22), and we have demonstrated the same classification accuracy at 3T and 7T for the SCA1 cohort that was scanned on both scanners (23), justifying the use of the 3T platform in future trials.

2.3 Existing Literature:

Conventional structural MRI has been the standard of care to monitor the characteristic cerebellar and brainstem atrophy in patients with SCA1 and SCA3. However, conventional MRI has limited sensitivity at the premanifest stage (24, 25) because macrostructural changes are the end point of a cascade of events that lead to neuronal death. Mounting evidence indicates that the underlying cellular changes start years before clinical onset and irreversible neurodegenerative damage detectable by conventional MRI (26). Therefore, we focus on imaging biomarkers that are sensitive to these early pathological changes, which are reliable, reproducible, and can gauge treatment effects objectively and quickly. Whereas a few Positron Emission Tomography (PET) studies have demonstrated hypometabolism in premanifest SCA (19), PET is significantly more expensive and less readily available than MRI and involves radiation exposure. Hence, we will utilize MRI modalities that have been widely validated in SCAs and are ready for use in a multi-site setting.

Macrostructural and microstructural MR measures are sensitive to progressive morphological alterations in SCA. Using MRI scanners of 1.5 Tesla (T) field strength, the European Ataxia Study Group (EASG), has established the sensitivity of volumetric MRI to morphometric alterations in the most common SCAs in both single- and multi-site investigations (27-29). Morphometric T₁-weighted MRI data analyzed with a 3D volumetric method and voxel based morphometry (VBM) reveal prominent reductions in gray (GM) and white matter (WM) in the cerebellum and brainstem in SCA1 and SCA3 (29). While these macrostructural changes correlate with

SARA (29), the volumetric measures were more sensitive to change than SARA in a longitudinal multi-site study (30), providing a strong rationale to supplement the clinical outcome assessments (COAs) with these objective, non-invasive MR markers in trials. Most importantly, a large multi-site EASG study of at-risk subjects (SARA<3) showed significant GM loss in the brainstem and cerebellum in SCA1 mutation carriers and subtle brainstem volume loss in SCA3 mutation carriers (18).

Regional damage to WM in SCA1 and SCA3 has been demonstrated by diffusion tensor imaging (DTI) by many groups (31-34). However, the standard DTI model may miss subtle WM alterations and does not resolve crossing fibers, limitations that are overcome by high angular resolution diffusion imaging (HARDI). Our preliminary data described in section 2.2, together with prior reports (31-34), warrant validation of diffusion MRI in large patient cohorts in a multi-site longitudinal setting.

MRS biomarkers reflect the clinical status, progression, and reversal of pathology in SCA. Over the past 7 years, the University of Minnesota (UMN) group has demonstrated the sensitivity of MRS-measured neurochemical levels to progression (35) and reversal (36, 37) of SCA pathology in animal models.

Neurochemical abnormalities were detected at the presymptomatic stage (35) and prior to the appearance of gross histopathological changes (38). Importantly, MRS detected treatment effects in a conditional transgenic SCA1 mouse model with the same sensitivity/specificity (areas under the curve [AUC]=0.97-0.98 in receiver operating characteristic [ROC] analyses) as invasive outcome measures (histology and qPCR) and with much higher sensitivity/specificity than standard motor behavioral assessment (Rotarod, AUC=0.72) (37).

In human subject studies, we reported robust neurochemical alterations, reflecting neuronal loss or dysfunction (N-acetylaspartate [NAA], glutamate) and gliosis (myo-inositol) in the cerebella and brainstem of patients with SCAs, including SCA1 and SCA3 (39-41). Similar to morphometric measures, the neurochemical alterations measured by MRS correlated with SARA (39, 41), but were more sensitive to change than SARA in a longitudinal 3T study (42). We further showed excellent within- (22) and between-site (43, 44) reproducibility of MRS measures in healthy volunteers: Between session test-retest CV of $\leq 5\%$ are obtained from a cerebellar volume-of-interest (VOI) for 5 major neurochemicals at 3T (22) and identical neurochemical profiles from the cerebellum and brainstem are obtained on different 3T scanners, allowing pooling of multi-site data (43).

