5.0 Procedures Involved

5.1 Study Design:

Premanifest and early-phase subjects with the SCA1 or SCA3 mutation and healthy controls will be enrolled. Subjects will be scanned up to 6 times during the U01 period, at baseline, 6 months, 1 year, 18 months, 2 years and 3 years. With this scanning schedule, we aim to capture any imaging alterations as soon as they occur, and to obtain rich data for best trial readiness. We will enrich the SCA1 and 3 cohorts by inviting participants with an estimated time to onset (20) within 10 years. De-identified clinical data on the same subjects will be available from the multi-site U01 study for correlations with the MR measures. The main clinical assessment (SARA) will also be administered at UMN.

5.2 Study Procedures:

Screening: Subjects will be identified from among the enrollees of the multi-site U01 clinical study (performed under a central IRB and *not* covered under the current IRB protocol), screened clinically by the lead site of the U01 grant (Houston Methodist Research Institute) for disease stage and referred to UMN for MR safety screening prior to enrollment. For screening, the research team will utilize the CMRR Center's screening tools and adhere to the screening SOP during enrollment of all research participants in this protocol. The CMRR Center's screening tools and SOP are IRB approved under the CMRR Center Grant (HSC# 1406M51205) and information regarding screening procedures is publicly available on the CMRR website ([CMRR Policies / Procedures](#)).

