The sample size calculation for this study is based on imaging data that will be acquired at 6 imaging sites, for a total sample size of 100 subjects, namely a 30 (20 premanifest and 10 early-phase) subjects with the SCA1 mutation, 40 (27 premanifest and 13 early-phase) subjects with the SCA3 mutation and 30 controls. The at-risk subject study by the EASG group, which included imaging data from 26 SCA1 mutation carriers and 9 SCA3 mutation carriers, reported significant VBM alterations in SCA1 and trends in SCA3 (18). Based on these data, a Wilcoxon rank sum test will have 95% power to show a difference between controls (mean = 0.018, SD = 0.019) and SCA (mean = 0.016, SD = 0.0019) with 30 subjects per group ($\alpha = 0.025$ to take into account the two comparisons of SCA1 and SCA3 versus controls, two-tailed test). Note that this power computation is conservative since the EASG study included only at-risk subjects, whereas the current study will include both premanifest and early manifest patients. In addition, based on our MRS preliminary data described above, a Wilcoxon-Mann-Whitney test will have 94% power to show a difference in NAA at baseline between premanifest subjects who have disease onset within the 5 years of the U01 (conservatively estimated at 1/3 of the patients i.e. $n=7$, mean = 1.2) and those patients who remain in the premanifest stage ($n=14$, mean = 2) for the SCA1 group (standard deviation of 0.4, $\alpha = 0.05$, two-tailed test). We will recruit a larger sample size for the SCA3 cohort because: 1) imaging alterations did not reach significance for SCA3 mutation carriers in the at-risk EASG study; 2) the diffusion MRI abnormalities in our preliminary data (see section 2.2) were less pronounced in SCA3 than those in SCA1; and 3) SCA3 is the most common SCA, enabling recruitment of a larger cohort.

15.3 Statistical Analysis:

To compare the imaging biomarkers between SCA1, SCA3 and control cohorts, globally and in a pairwise fashion, we will use Wilcoxon rank sum test. In addition, premanifest carriers and early-stage patients will be compared using Wilcoxon rank sum test. Within each SCA group, premanifest and manifest patients will be compared regarding the biomarkers at baseline and during follow-up. If this approach is not conclusive, cluster approaches will be carried out. Sex will be considered as a biological variable to assess potential sex-based differences in imaging results.

15.4 Data Integrity:

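### The one powered onset contrast (baseline NAA, SCA1 converters v non-converters) leaves out CAG repeat and age, so it cannot show the improvement over the CAG/age estimate that section 2.1 claims

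*Protocol*

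**What the plan says.** Section 2.1 describes the study as one "with a goal to predict disease onset in premanifest individuals based on a multi-parametric model that incorporates imaging biomarkers". It notes that a model based on CAG repeat size and current age already exists, calls onset age highly variable at a given repeat length, and concludes that "measuring cerebral disease onset by noninvasive imaging is bound to substantially improve the estimation of onset age of manifest disease". It adds that this would let future trials recruit the premanifest carriers closest to onset.

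Section 5.1 uses the same model for recruitment: "We will enrich the SCA1 and 3 cohorts by inviting participants with an estimated time to onset (20) within 10 years".

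Section 2.2 reports from the 7T MRS study that "premanifest mutation carriers were distinguished from controls if the time-to-onset, estimated based on CAG repeat size and current age (20), was 10 years or less"; this held for 6 of 9 carriers. NAA is listed there among the metabolites driving the classifications.

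Section 15.2 gives the onset contrast: "a Wilcoxon-Mann-Whitney test will have 94% power to show a difference in NAA at baseline between premanifest subjects who have disease onset". Onset here means onset during the five-year grant, and the comparison is with those who stay premanifest. The inputs are 7 converters (mean 1.2), 14 non-converters (mean 2), SD 0.4 and two-sided alpha 0.05, for SCA1 only.

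Section 15.3 lists Wilcoxon rank sum comparisons, cluster approaches if these are inconclusive, and sex as a biological variable. No section gives CAG repeat, age or estimated time to onset a role as covariate, stratum or comparator.

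**The concern.** A claim to improve on a named predictor can be tested only with that predictor in the analysis. Converters will on average have had a shorter CAG/age-estimated time to onset at baseline. The protocol's own preliminary data suggest that neurochemistry changes with that estimate. A lower NAA in converters could therefore reflect, at least in part, what CAG and age already say.

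At stake is the use that section 2.1 has in mind. A positive unadjusted result could be read as a reason to scan carriers in order to select them for trials, when a calculation from repeat length and age might do part or all of the same job.

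**Working it through.** **1. The stated power.** Standardised difference: (2 − 1.2)/0.4 = 2.0.

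- Normal approximation: 2.0/√(1/7 + 1/14) = 2.0/0.463 = 4.32; 4.32 − 1.96 = 2.36; power 99.1%.
- Noncentral t: 98.4%.
- Simulated Wilcoxon-Mann-Whitney with exact p: 97.5%.
- Noether: P(X<Y) = Φ(2/√2) = 0.921; √(12 × 1/3 × 2/3 × 21) × 0.421 − 1.96 = 1.19; power 88.4%.

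The stated 94% is not reproduced exactly. It lies between the Noether figure and direct simulation and is mildly conservative against the latter. The point does not depend on it. (7 + 14 = 21, whereas the same section lists 20 premanifest SCA1 subjects; 7 v 13 gives 97.3%.)

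**2. A marker that only mirrors CAG and age.** From the protocol: 21 subjects, 7 converters, a 0-10 year window, a two-sided 5% test. Assumed, because the documents give neither the accuracy of the CAG/age model nor its correlation with NAA:

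- estimated time to onset P is uniform on 0-10 years;
- true time to onset is T = P + error, with error SD s;
- converters are the 7 subjects with the earliest T;
- marker M = r × standardised P + √(1 − r²) × noise, so that M says nothing about T once P is known.

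Share of simulated studies in which the unadjusted rank test is significant, s = 2-4 years:

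| r | all subjects kept | those with T already past at baseline excluded |
|---|---|---|
| 0.5 | 15-28% | 13-25% |
| 0.7 | 27-58% | 21-51% |

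At r = 0.3 the range is 7-13%. At s = 8 years it is about 4-14%. The exclusion matters because a person past onset is not premanifest. Converters are then about 2.3-3.7 years closer to estimated onset than non-converters, against 2.8-4.0 years without it. With P as a covariate in a linear model, the rate is about 5%.

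**3. Role of enrichment.** Same type of marker, r = 0.7, past-onset subjects excluded, noise held fixed:

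| window for P | s = 3 | s = 5 | s = 8 |
|---|---|---|---|
| 0-10 years | 32% | 14% | 7% |
| 0-20 years | 92% | 67% | 33% |

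The narrower window gives less false credit.

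**4. Size of difference that mirroring produces.** At r = 0.3-0.7 and s = 2-4 years a mirror marker separates the groups by about 0.3-1.1 SD on average, against the 2.0 SD assumed in section 15.2.

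**5. Power of the adjusted analysis.** Keep the total NAA separation at 2 SD. Let estimated onset separate the groups by δ SD and correlate ρ with NAA within groups. The adjusted difference is 0.4 × (2 − ρδ). For ρ = 0.3-0.7:

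| δ | adjusted NAA difference | power |
|---|---|---|
| 0.5 | 0.74-0.66 | 96-99% |
| 1.0 | 0.68-0.52 | 86-89% |
| 1.5 | 0.62-0.38 | 58-74% |

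**The case against.** The strongest reply is that the improvement claim is background rationale. Onset prediction is neither among the objectives in section 1.1 nor an endpoint in section 3. The converter comparison appears only in the power section, is not restated in section 15.3, and is nowhere said to demonstrate improvement over the CAG/age model. Section 2.1 also names a multi-parametric model that could include CAG and age, and an unseen analysis plan could adjust. Repeat length is to be accessed (section 18.2), although for clinical correlates of the MR measures.

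Much of this stands, and it limits the weight of the point. The NAA test is not the only onset analysis foreseen. It is, however, the only one that the protocol specifies and powers, and its form does not answer the stated goal. The issue is what the protocol fixes, not detail that it leaves open.

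Three stronger readings are tempting and are not supported:

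- A reader might infer that the unadjusted test will separate the groups whatever imaging adds. Under most of the assumptions above a pure mirror marker is non-significant in the majority of studies, and the protocol's remark on highly variable onset ages points towards the larger model errors, where the effect is small.
- A reader might blame the enrichment. Restricting estimated onset narrows the confounder. It would handicap the CAG/age model in a side-by-side comparison of discrimination, but the protocol plans no such comparison.
- A reader might dismiss any positive NAA result. Mirroring alone would rarely produce the 2 SD difference that section 15.2 expects.

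**Conclusion.** The point holds in a limited form. The protocol states a goal of improving on the CAG/age estimate, and the one onset contrast it powers cannot show such an improvement. The excess of significant results for a marker with no added information runs from negligible (about 4-14% at a model error SD of 8 years) to substantial (21-58% at SD 2-4 years and correlation 0.7), against a nominal 5%. These rates rest on an assumed model error, an assumed marker-estimate correlation and a uniform spread of estimated onset over 0-10 years. Without figures for the first two, the documents do not allow a narrower range. The defect is the missing comparison with the existing estimate. It leaves the primary aim of biomarker validation untouched and is worth correcting because the remedy is cheap.

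**What to change.** In section 15.3, keep the unadjusted converter v non-converter test of baseline NAA as a description. Add a regression of baseline NAA on conversion status with CAG/age-estimated time to onset as a covariate. Rest any claim of improved onset prediction on the adjusted conversion term. In section 15.2, state that the 94% applies to the unadjusted test only.

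No new data are needed: the estimate is already used for invitation and repeat length is already accessed. The cost is one degree of freedom (residual 21 − 2 = 19 becomes 21 − 3 = 18) and some power. Adjusted power is about 86-99% if estimated onset separates the groups by 0.5-1.0 SD, and falls to about 58-74% at 1.5 SD. The protocol should acknowledge that loss. With about 7 SCA1 converters expected, one marker plus this one covariate is about as much as the data will carry.
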